9.14 Deviation Handling

A study deviation is defined as an event within a study that was not conducted according to the clinical investigation plan, CTA, EC policies or applicable standards, laws and regulations.

The PI/ Sub investigator may not deviate from the CIP unless the deviation is necessary in an emergency

situation to protect the rights, safety and wellbeing of the subject. Or due to an unforeseen circumstance that is beyond the PI/ Sub investigator's control (e.g., subject failure to attend a scheduled follow up visit, inadvertent errors, equipment failure). All deviations must be documented on CRF whether an inadvertent occurrence or taken to protect the subject in an emergency. Multiple deviations of the same type at the same visit may be reported on one CRF.

Refer to section 14.9.1 for deviation reporting requirements .

Deviations include, but are not limited to, the following:

- Failure to obtain subject's informed consent prior to beginning study activities
- Subject does not meet inclusion/exclusion criteria, but continues with the scheduled visits and aDBS setup.
- Failure to report AEs or Device Deficiencies
- Failure to collect CIP-required assessments
- Subject missed visit or visit outside of window

Deviations will be reviewed by the PI on an ongoing basis. The PI will assess the significance of all deviations for the study and evaluate the need for any corrective and/or preventative actions (e.g. amend the CIP, conduct additional training, terminate the study).

9.15 Subject Exit, Withdrawal or Discontinuation

Subjects will discontinue the study following completion of all study visits.

If a subject discontinues from the study prior to normal completion, the CRFs for visits that have occurred up to the point of withdrawal as well as the study exit CRF must be completed.

9.15.1. Study Exit

A study exit CRF is required for all subjects. Subjects are urged to remain in the study as long as possible but may be exited from the study for any of the following situations:

- Study completed
- Subject lost to follow-up
- Subject death
- Subject's DBS Therapy System permanently explanted (i.e., neurostimulator, lead, extension)

- Subject did not meet inclusion/exclusion criteria
- Subject chooses to withdraw (e.g., consent withdrawal, relocation to another geographic location)
- PI/ Sub investigator deems withdrawal necessary (e.g., medically justified, inclusion/exclusion criteria not met, failure of subject to maintain adequate study compliance)

The PI/ Sub investigator will attempt to collect the following information prior to the subject's early discontinuation from the study:

- Adverse event and device deficiency assessment
- Programming session report, with device interrogation and BrainSense data included in the JSON session data report upload
- A brief description of why the subject discontinued (if applicable)

9.15.2. Study Completed

At the completion of Follow-up Phase Visit6, subjects will be exited from the study. Both the CRFs for Follow-up Phase Visit6 and a Study Exit CRF need to be completed. Suggested language:

9.15.3. Lost to Follow-up

A subject is considered to be lost to follow-up if at least two attempts to contact the subject are unsuccessful. The method of attempt (e.g., two letters, two phone record or two emails) must be documented in the subject's medical record.

9.15.4. Study Exit Criteria in Individual Subject

9.15.4.1 Subject Chooses to Exit (i.e. Revokes Consent)

A subject can withdraw from the study at any time. If the subject revokes consent, the study site is required to document the reason for exit on the Exit CRF.

If possible, the following data should be collected prior to subject withdrawal:

- Adverse event and device deficiency assessment
- Final device interrogation and data upload
- Export JSON Session Data
- A brief description of why the subject discontinued (if applicable)

9.15.4.2 Investigator Withdraws Subject

- After enrollment if the subject doesn't meet the inclusion or exclusion criteria
- When the PI/ Sub-investigator decides to discontinue or the subject wishes to discontinue due to the adverse event
- When it becomes difficult to continue the study due to worsening of the underlying disease
- When the subject has difficulties in continuous visits due to moving, changing hospitals, busy schedules, etc
- If the subject becomes pregnant or is suspected of becoming pregnant
- When the PI/ Sub-investigator determines the necessity of discontinuing from the study

It is recommended that PI/ Sub investigators discuss any withdrawals with the study team prior to withdrawing subjects.

If a withdrawal by the PI/ Sub investigator is necessary, the following data should be collected prior to subject withdrawal if possible:

- Adverse event and device deficiency assessment
- Final device interrogation and data upload
- Export JSON Session Data
- A brief description of why the subject discontinued (if applicable)

10. Risks and Benefits

10.1 Potential Risks

10.1.1. Potential DBS risks

Deep Brain Stimulation Therapy is a reversible procedure (i.e., the stimulation can be turned off or the device can be removed most cases) that is able to adjust the stimulation to minimize or reverse complications and maximize therapeutic effects.

The risks, precautions, warnings, cautions, and contraindications associated with the Medtronic DBS Therapy and each system component are included in the package inserts.

10.1.2. Pregnancy

The safety of neurostimulation systems is unknown for pregnancy, unborn fetus, or delivery. Because the risks to the subject and/or unborn child while receiving neurostimulation are unknown, female subjects of childbearing potential must confirm a non-pregnant at screening visit and agree to use a medically acceptable method of birth control if female of childbearing potential, and if sexually active. Should a pregnancy occur during the study, the subjects are instructed to notify their PI/ Sub investigator immediately and the PI/ Sub investigator will notify Medtronic in a timely manner. Careful considerations of the risks and benefits of continuation in the study will be weighed by the subject and their PI/ Sub investigator.

10.1.3. Potential aDBS risks

The primary function of the aDBS is to adjust stimulation amplitude within clinician-defined stimulation limits. The risks of adaptive DBS are no different than the risks of commercially available cDBS risks, which are not increased due to participation in the study.

10.1.4. Potential Study Procedures Risks

Randomization, single-blind and crossover will be conducted in the study. Potential risks related to study procedures include:

- The safety of DBS is unknown for pregnancy, unborn fetus, or delivery. If a subject is or a subject becomes pregnant, there may be risks to the subject or the subject's unborn child that are not yet known.
- As a result of the mode change (aDBS and cDBS) subjects may experience differences in therapeutic effects and changes in condition between aDBS and cDBS
- Subjects may experience skin irritation from the Apple watch. Should irritation occur, the subject should remove the watch
- There may be risks or side effects which are unknown at this time.

10.1.5. Potential Study Procedure Inconveniences

Potential study procedure inconveniences include:

- The patient's assessments, such as QOL questionnaire, subjects are required to complete for the study may be burdensome.
- The patient's assessments that are required for the study may request information of a personal

nature

- The patients feel a burden on the operation of Apple Watch / iPhone required in this study.

10.2 Risk Minimization

The PI provides study personnel with CIP training to minimize the potential risks associated with this study.

The PI/ Sub investigator will carefully observe the subjects and be actively involved in the follow-up of the subjects.

When aDBS causes an uncomfortable stimulus to the subject, the subject can switch from aDBS to cDBS as needed.

10.3 Potential Benefits

All of the medical devices used in this study are approved for indication and covered by insurance for the subjects of this study, and the treatment methods of any group are treatment methods that can be performed as everyday insurance medical treatment. In addition, since all medical expenses including drug costs during the study period of the subject are paid by the patient's insurance and the patient's own expense, the special medical and economic aspects obtained by the subject participating in the study that there is no benefit. The information obtained from this clinical study may be useful to other patients in the future.

10.4 Risk-Benefit Rationale

The benefit of the study lies in the knowledge to be gained from the results and the potential to improve future DBS therapies. Deep Brain Stimulation Therapy including adaptive therapy for PD with Percept PC system has obtained regulatory approval and is covered by insurance, and both treatment methods can be performed as daily insurance medical treatment. There is no direct benefit expected to arise from a subject's participation in this study, but there may be risks from the study procedure. Measures have been taken to minimize the risks and all the potential risks in this study have been controlled to a level as far as possible.

11. Adverse Event and Device Deficiencies

11.1 Adverse Events

All DBS System Components which are used for this study are approved with demonstrated evidence of safety and effectiveness for their intended use. Therefore, the following AEs will be collected for safety analyses in this study:

- Stimulation-related adverse events
- Serious adverse events for which the relationship with Percept PC cannot be ruled out
- Any-cause death
- An Unanticipated Serious Adverse Event (USAE) in which the relationship with the use of the study device cannot be ruled out completely.

AE definitions are provided in Table 2. All reportable AE information for this study will be collected throughout the study duration, starting at the time of signing the IC.

11.2 Device Deficiency

The following Device Deficiency (DD) will be collected for safety analyses in this study

- Device (Percept PC) deficiencies that potentially could have led to a serious adverse event

DDs that did not lead to a serious adverse event but could have led to a serious adverse device effect include the following

- if either suitable action had not been taken
- if intervention had not been made
- if circumstances had been less fortunate

The DD definition is provided in Table 2. Reportable DD information will be collected throughout the study after signing the IC and reported to Medtronic on the DD eCRF. Note that DD that result in an AE to the subject should be captured as an AE only.

11.3 Correspondence to subjects

In the event of AE, the PI/ Sub investigator will take appropriate measures, such as treatment and discontinuation of use of the device, as necessary to ensure the safety of the subjects. If treatment is required, inform the subjects to that effect.

11.4 Processing Updates and Resolution

For any changes in status of a previously reported AE or DD (i.e. change in actions taken, change in outcome, change in relatedness), information needs to be updated on, or added to the original AE or DD CRF. All AEs must be followed until the AE has been resolved, is confirmed no further actions planned if unresolved, the subject dies or exits the study, or until study closure, whichever occurs first.

At the time of study exit, all collected AEs that are unresolved must be reviewed and an update to the original AE must be reported.

11.5 Definitions/Classifications

This study will be conducted following Japan Ethical guidelines for human life science and medical research and will collect the Adverse Events and Device Deficiencies specified in this protocol from the time of consent through study exit/discontinuation.

AEs and DDs which are collected in this study will be classified by Medtronic and/or the PI/ Sub investigator according to the standard definitions as outlined below.

Table 2: Adverse Event and Device Deficiency Definitions

General	
Adverse Event (AE)	An unfavorable and unintended injury and illness or sign of such (including an abnormal laboratory finding) caused to research subjects, regardless of whether there is or is not any causal relation with the research implemented. (Ethical guidelines for human life science and medical research, Chapter 1, Part 2, (32)) (ISO 14155:2020 section 3.2 is equivalent to this AE definition)
Device Deficiency (DD)	Any influences of an undesirable condition for a medical device such as breakage and malfunction, etc. Which stage among design, manufacturing, marketing, distribution, and use caused the device deficiency is irrelevant. (Ministerial Notification on Reporting of Side Effect, etc. of Pharmaceutical Product, etc. dated October 2, 2014)

	(ISO 14155:2020 section 3.19 is equivalent to this DD definition)
Relatedness	
Relationship of Adverse Events	
The relationship of an adverse event will be classified as device-related, therapy/stimulation-related, procedure-related, related to the disease under study, and/or related to an underlying condition other than the disease under study based on the following definitions:
 
 • Device Related: An adverse event that results from the presence or performance (intended or otherwise) of the DBS system or any of the DBS system components • Procedure Related: An adverse event that occurs due to any procedure related to the surgical modification, or explant of the DBS system or any of the DBS system components. • Therapy/Stimulation Related: An adverse event related to therapy delivery by the DBS system (i.e. stimulation). Normally therapy related events resolve when the device is turned off or reprogrammed. • Related to the disease under study: An adverse event that is caused by Parkinson's disease • Related to an underlying condition other than the disease under study: An adverse event caused by a condition other than Parkinson's disease 
Each of the relatedness classifications will be assessed for causality using four different levels of causality based on the following definitions:
 
 • Not Related: relationship to the device or procedures can be excluded when: 
 ▪ the event is not a known side effect of the product category the device belongs to or of similar devices and procedures; ▪ the event has no temporal relationship with the use of the study device or the procedures; ▪ the serious event does not follow a known response pattern to the medical device (if the response pattern is previously known) and is biologically implausible; ▪ the discontinuation of medical device application or the reduction of the level of activation/exposure – when clinically feasible and reintroduction of its use (or increase of the level of activation/exposure), do not impact on the serious event; ▪ the event involves a body-site or an organ not expected to be affected by the device or procedure; ▪ the serious event can be attributed to another cause (e.g. an

	
underlying or concurrent illness/ clinical condition, an effect of another device, drug, treatment or other risk factors);
 
▪ the event does not depend on a false result given by the study device used for diagnosis, when applicable;▪ harms to the subject are not clearly due to use error;▪ in order to establish the non-relatedness, not all the criteria listed above might be met at the same time, depending on the type of device/procedures and the serious event 
• Possible: the relationship with the use of the study device is weak but cannot be ruled out completely. Alternative causes are also possible (e.g. an underlying or concurrent illness/ clinical condition or/and an effect of another device, drug or treatment). Cases where relatedness cannot be assessed or no information has been obtained should also be classified as possible.• Probable: the relationship with the use of the study device seems relevant and/or the event cannot reasonably be explained by another cause, but additional information may be obtained• Causal relationship: the event is associated with the study device or with procedures beyond reasonable doubt when:
▪ the event is a known side effect of the product category the device belongs to or of similar devices and procedures;▪ the event has a temporal relationship with study device use/application or procedures;▪ the event involves a body-site or organ that
○ the study device or procedures are applied to;○ the study device or procedures have an effect on;○ the serious event follows a known response pattern to the medical device (if the response pattern is previously known);▪ the discontinuation of medical device application (or reduction of the level of activation/exposure) and reintroduction of its use (or increase of the level of activation/exposure), impact on the serious event (when clinically feasible);▪ other possible causes (e.g. an underlying or concurrent illness/clinical condition or/and an effect of another device, drug or treatment) have been adequately ruled out;▪ harm to the subject is due to error in use;▪ the event depends on a false result given by the study device used for diagnosis, when applicable;▪ in order to establish the relatedness, not all the criteria listed above
--	---

	
might be met at the same time, depending on the type of device/ procedures and the serious event.
 
Events are considered “related” to the study medical device if their relationship to the device, procedure, or therapy is classified as “possible”, “probable”, or “causal”.

Seriousness	
Serious Adverse Event (SAE)	
Of the above-defined AE, an event that:
 
 1) Results in death 2) Is life-threatening 3) Requires inpatient hospitalization or prolongation of existing hospitalization 4) Results in persistent or significant disability or incapacity, or 5) Is a congenital anomaly/birth defect to offspring. 
(Ethical guidelines for human life science and medical research, Chapter 1, Part 2, (33)) (ISO 14155:2020, 3.45 is equivalent to this SAE definition)

Unanticipated* Serious Adverse Event (USAE)	
Of the above-defined SAE, an event not consistent with the information in the research protocol, the document used for obtaining informed consent, or not consistent with the severity described in such, even if there is any description about the event.
 
(Ethical guidelines for human life science and medical research, Chapter 1, Part 2, (34))

Device Deficiency with SADE potential	
DDs that did not lead to a serious adverse event but could have led to a serious adverse device effect include the following
 
 • if either suitable action had not been taken • if intervention had not been made, or • If circumstances had been less fortunate

* Anticipated AE/DD: Refer to the description regarding AE/DD in the package insert.

The following are not considered an AE for the study.

- Pregnancy
- Documented pre-existing conditions / planned treatment at the time of enrollment; unless the intensity, duration, or frequency of the condition is worsened from the time of enrollment
- Planned examination at the time of enrollment

- Programming adjustment or therapy suspension (could be an action taken as a result of an AE)
- Transient (acute) stimulation-induced effects that occur during programming sessions or while running aDBS that resolve with or without programming adjustments prior to the subject leaving a study follow-up visit and do not require further follow-up or medical care outside of the visit
- Neurostimulator replacement for battery depletion as disclosed in the product labeling (documented as a system modification)
- Worsening patient-questionnaire reported outcome scores (e.g. EQ-5D-5L, PDQ-39)
- Expected side-effects of Parkinson's disease medication

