In the initial stages of PD, motor symptoms are often well controlled using dopaminergic drugs. However, chronic use of these levodopa medications over a 5-10 year period is associated with symptom fluctuations, dyskinesia and other motor complications in up to 80% of PD patients.⁴ These complications may be equal to or worse in severity than the motor impairment caused by the disease itself.⁸ Deep Brain Stimulation (DBS) Therapy may be used to treat some of the motor complications of PD that are not adequately controlled with medication. DBS is a surgical intervention that involves the placement of electrodes in targeted areas of the brain. These electrodes are arranged on a lead and are connected to an implanted neurostimulator that delivers mild electrical pulses to targeted brain areas. Once patients are implanted with the DBS device, clinicians may adjust the electrical stimulation parameters to obtain maximal symptom relief and minimize stimulation-induced adverse effects. The use of DBS in the subthalamic nucleus (STN) and globus pallidus interna (GPi) has been shown to improve symptoms of PD.^{4,9,10,11,12,13,14,15,16,17} Several multicenter, randomized controlled trials conducted in the United States, Europe, and in several other geographies worldwide provide evidence of its effectiveness.^{18,19,20,21,22,23,24} Deep Brain Stimulation Therapy is currently delivered in a continuous fashion (cDBS) where stimulation settings are constant over time and do not adjust to fluctuations in symptoms typically experienced by Parkinson's disease patients during medication On and Off states. During On-medication states, the addition of stimulation using cDBS is thought to adversely affect dyskinesias and other side effects experienced by the patient.²⁵ To make DBS more responsive to an individual patient's clinical state, investigators have explored the use of adaptive DBS (aDBS) therapy.

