In recent years, research has been conducted to test the feasibility of using aDBS Therapy where the stimulation adjusts automatically based on LFPs in the basal ganglia. Based on evidence that beta LFPs decrease in response to increasing stimulation, two slightly different aDBS control mechanisms have been utilized in these studies. The first is a scalar approach (i.e., dual threshold aDBS mode) whereby stimulation amplitude incrementally adjusted between upper and lower, clinician-defined therapeutic limits to maintain beta LFP within a defined range.^{45,46,47} The second is a binary approach (i.e., single threshold aDBS mode), whereby stimulation switches on when the beta LFP exceeds a preset threshold and switches off when the LFP falls below the preset threshold.^{25,48,49,50} Clinical studies using both single and dual threshold aDBS control mechanisms support the technical feasibility of using beta LFP signals as a signal of interest for aDBS.^{45,46,47,48,49,50,51,52,53,54}

Evidence from single center feasibility studies has demonstrated that aDBS is at least as efficacious as cDBS based on UPDRS III motor scores and could potentially be up to 27% more effective.^{47,48,49} aDBS may also reduce stimulation-induced adverse effects such as dyskinesia and speech impairment. In multiple studies, PD patients receiving aDBS showed less dyskinetic effects compared to cDBS, potentially by reducing the sum effect of stimulation and medication.^{25,52,54} Regarding speech, one study of 10 subjects showed a clinically meaningful improvement in speech intelligibility with aDBS over cDBS.⁵⁰ Overall aDBS was well tolerated in freely moving PD subjects both On and Off medications for up to 8 hours.^{47,49,52,53,55} In addition, multiple studies showed a significant reduction in the power usage with aDBS compared to cDBS, averaging about 50% of the power demand of standard cDBS Therapy.^{45-49,52,54}

Although the subjects and conditions of the individual studies assessing aDBS vary, these studies have consistently shown the feasibility of using aDBS controlled by STN beta LFP feedback and its potential to effectively reduce PD symptoms while reducing side effects and increasing battery longevity.

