12.6 Safety Assessment

To assess safety in following items:

- Stimulation-related adverse events during the aDBS treatment phase.

- Serious adverse events which occur through the study after consent and for which the relationship with Percept PC cannot be ruled out.
- Any-cause death throughout the study.
- Device (Percept PC) deficiencies that potentially involve a serious adverse event throughout the study: for all subjects

Stimulation-related adverse events will be summarized during the aDBS treatment phase for all subjects, with listings individualized by aDBS mode and cDBS.

Serious adverse events, adverse events, and device deficiencies that occur from the consent through study exit/discontinuation will be summarized for all enrolled subjects. The denominator will include the appropriate number of subjects for each respective phase and period. Events will be summarized by number of events, number of subjects who experienced the event, and percentage of subjects who experienced the event.

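### The list of events that do not count as AEs treats aDBS and cDBS differently and has no worsening rule for medication-linked symptoms, so under-recording that differs by mode is possible

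*Protocol*

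**What the plan says.** After Table 2, Protocol 11.5 lists what is not an AE in this study. Three bullets matter here.

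- **Transient effects.** The bullet covers "Transient (acute) stimulation-induced effects that occur during programming sessions or while running aDBS that resolve with or without programming adjustments", and continues with the limit "prior to the subject leaving a study follow-up visit and do not require further follow-up or medical care outside of the visit".
- **PD medication.** The whole bullet reads "Expected side-effects of Parkinson's disease medication".
- **Pre-existing conditions.** These are excluded "unless the intensity, duration, or frequency of the condition is worsened from the time of enrollment".

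The first safety item in Protocol 4.1.3 is stimulation-related adverse events during the aDBS treatment phase. Protocol 12.6 plans this output: "Stimulation-related adverse events will be summarized during the aDBS treatment phase for all subjects, with listings individualized by aDBS mode and cDBS". SAP 7.10 adds counts of events and subjects, and percentages, by phase and period. Neither document plans a safety test, margin or power calculation.

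On dyskinesia, Protocol 3.1 says that chronic levodopa use "is associated with symptom fluctuations, dyskinesia and other motor complications in up to 80% of PD patients". The same section says that "aDBS may also reduce stimulation-induced adverse effects such as dyskinesia and speech impairment", and that adding cDBS in the On-medication state is thought to affect dyskinesias adversely.

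**The concern.** A by-mode listing is informative only if the same experience is recorded the same way in both modes. Here the written case definition depends on the mode that is running. The person applying it knows the mode: only subjects are blinded, the investigator programs the assigned mode (Protocol 9.7, 9.8.1), and the investigator identifies reportable events (Protocol 11.6).

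The medication bullet raises a second problem. The protocol attributes dyskinesia both to levodopa and to stimulation, and expects it to differ between modes. If it worsens after a mode change, two bullets of one list give opposite answers and no rule says which prevails. At stake is whether the listings can support a descriptive statement about stimulation-related events on aDBS compared with cDBS.

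**Working it through.** The documents give no AE rate and no figure for the safety comparison, so there is no plan figure to reproduce. The check sets the texts side by side.

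**Step 1: the transient bullet by situation.** Take an effect that settles before the subject leaves the visit and needs no further care.

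| Situation | aDBS | cDBS |
|---|---|---|
| During a programming session | Excluded | Excluded |
| Stimulation running, no programming | Excluded | Remains an AE |

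The second row is the asymmetry. The limiting clause applies to both rows and does not remove it.

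**Step 2: how far the second row reaches.** The clause fixes the time of resolution, not the place of onset. Read narrowly, it covers effects that start and stop in clinic while aDBS runs. Read broadly, it could cover an effect that began at home on aDBS and settled before the subject left the next visit. The text does not decide between these readings. It also does not say whether a follow-up visit means any study visit or only Visits 4 to 6.

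**Step 3: the medication bullet against its neighbours.** Take dyskinesia present at enrollment that worsens after a switch of mode.

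- Pre-existing-condition bullet: it has worsened, so it is an AE.
- Table 2 relatedness: if a link to stimulation cannot be ruled out, the category is *possible*, which counts as related.
- Medication bullet: if it is seen as an expected drug effect, it is not an AE.

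The relatedness categories do not settle the conflict, because they classify adverse events and the list decides beforehand whether there is one. Table 2 likewise defines an SAE as a subset of AEs, so the medication bullet, read literally, can also remove a serious event.

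**Step 4: direction.** The transient bullet can only lower aDBS counts relative to cDBS. The medication bullet is worded the same for both modes and could hide events in either. Given the protocol's remark about cDBS and dyskinesia, it could hide cDBS events in particular. The two may work against each other.

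**Step 5: what the transient bullet alone could do (assumed values).** Let the true rate be the same number *r* in both modes, and let a fraction *f* of aDBS events meet an exclusion that has no cDBS counterpart. The recorded ratio of aDBS to cDBS is *r*(1 − *f*)/*r* = 1 − *f*.

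| Assumed *f* | Recorded ratio, true ratio 1 |
|---|---|
| 0 | 1.00 |
| 0.10 | 0.90 |
| 0.25 | 0.75 |
| 0.50 | 0.50 |

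The documents do not allow *f* to be estimated. On the narrow reading it may be close to 0.

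**The case against.** The case for leaving the list alone has real substance.

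- **The transient exclusion is narrow.** The words acute and visit, and the requirement of no further care, point to in-clinic effects, and programming sessions are covered in both modes. A reader might infer that transient stimulation effects are dropped for aDBS and kept for cDBS generally. The limiting clause and the programming-session wording do not support that. If a follow-up visit means Visits 4 to 6, when subjects are on aDBS, the randomized phase is untouched. That reading is strained, since programming also takes place at Visits 1 and 2, but the text does not exclude it.
- **The wording may have a reason.** cDBS settings are constant, so acute effects would mainly follow reprogramming, whereas aDBS changes amplitude by itself. This is plausible but unstated. It also does not justify a mode-specific rule, because the protocol itself describes cDBS effects that vary with medication state.
- **Worsening after a mode change is not naturally a drug effect.** PD medication is meant to stay stable through the treatment phase (Protocol 9.3), and the bullet does not name dyskinesia. A reader might infer that the protocol orders worsened dyskinesia to be dropped. It does not: that is one of two available answers. The missing precedence rule is what stands.
- **Dyskinesia is measured elsewhere.** UDysRS, MDS-UPDRS IV and Apple Watch data cover each period, so it would not vanish from the study. These are not a substitute for AE records, however. The additional objectives use the Complete Case set, which SAP 7.1.3 restricts to subjects with bilateral aDBS and complete data. Safety uses the As-Treated set. A subject who leaves early because of dyskinesia may have no pair of scores.
- **The by-mode output is descriptive.** This is correct, and it limits the consequence to how the listings may be read.

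**Conclusion.** The point holds as a defect in the recording rules. The transient bullet defines an AE differently by mode outside programming sessions. The medication bullet has no exception for worsening, seriousness or possible relation to stimulation, and it conflicts with the pre-existing-condition bullet. Under-recording that differs by mode is therefore possible in the safety listings.

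A reader might go further and say that the safety comparison is distorted in favor of aDBS. The documents do not show this: the net direction is unknown, and the size depends on how sites read the text. Nor does the 80% in Protocol 3.1 measure the problem. Applied to 20 completers it gives 0.80 × 20 = 16, but it is an upper figure for all motor complications under chronic levodopa. It is neither a dyskinesia rate in this sample nor a rate of excluded events.

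The conclusion rests on the wording alone and assumes that sites apply the list as written. It does not touch the primary or secondary endpoint. It should be fixed because the fix is cheap and removes a mode-dependent rule applied by an unblinded investigator.

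**What to change.** Amend two bullets in Protocol 11.5.

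1. **Transient effects.** Use one wording for both modes: exclude effects whose onset and resolution both fall within the same clinic visit, whether during programming or while aDBS or cDBS is running, and which need no further care. State which visits are meant.
2. **PD medication.** Exclude only effects that are non-serious, have not worsened since enrollment and are judged not related to stimulation. State that new or worsened symptoms after a mode change, and any serious event, are recorded and classified under Table 2.

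These edits change what is recorded, not how subjects are treated. SAP 7.10 can stay as it is, because its summaries take whatever the protocol defines as an AE. The cost is a protocol amendment, site retraining, a few more AE forms in a study of 20 to 30 subjects, and slightly higher AE counts.
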